13.0 CRITERIA FOR REMOVAL FROM STUDY

Subjects can leave the study at any time for any reason if they wish to do so without any consequences. The investigator can decide to withdraw a subject from the study for urgent medical reasons. Patients who withdraw before 120 days due to complications will be counted as failures for the patency objective. Patients who withdraw before 30 days will be counted as having experienced a complication for the purposes of the secondary objective.

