2.1 OBJECTIVES AND SCIENTIFIC AIMS

Primary objective:

The primary objective of this study is to assess patency of biliary drainage. In patients with plastic percutaneous drains this is defined as ability to remove plastic biliary drains within 1.5 months of the IRE procedure without need for reinsertion of a drain or stent. For patients with metal stents in place the definition of patent biliary drainage is 4-months without cholangitis post IRE procedure.

Secondary objective:

The secondary outcomes of interest are

- Duration of hospital stay
- Complications
- Quality of life
- Tumor response on CT imaging and blood biomarker response
- Time between IRE and start of palliative chemotherapy
- Duration of palliative chemotherapy
- Progression-free and overall survival
- Success rate of completing IRE (defined as percentage of planned pulses completed)

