14.1 BIOSTATISTICS

The primary objective of this study is to assess biliary drainage patency after IRE treatment of hilar cholangiocarcinoma. In patients with plastic percutaneous drains this is defined as ability to remove plastic biliary drains within 15 months of the IRE procedure without need for reinsertion of a drain or stent. For patients with metal stents in place the definition of patent biliary drainage is 4-months without cholangitis post IRE procedure.

We will enroll 20 patients. Mean patency is approximately 1.5 months for plastic stents and 4 months for metal stents. Assuming an exponential distribution time to failure, we extrapolate that the patency rate at 15 months for plastic stents and at 4 months for metal stents will approximately be 37% and we will use this number as our historical control rate. If 10 or more of the 20 patients we plan to enroll display patency (at 1.5 months for plastic and 4 months for metal stents) then we will recommend IRE for further study. This decision rule has 8% Type I error and 12% Type II error for distinguishing between patency rates of 37% and 65%.

The secondary outcomes of interest are:

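### The 120-day, complications-only withdrawal rule conflicts with the 1.5-month plastic-drain endpoint and leaves other early leavers without a stated patency status

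*Combined protocol and SAP*

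**What the plan says.** Section 13.0 lets subjects leave at any time and for any reason. It then gives two counting rules. For the primary objective: "Patients who withdraw before 120 days due to complications will be counted as failures for the patency objective". For the complication outcome: "Patients who withdraw before 30 days will be counted as having experienced a complication for the purposes of the secondary objective". The first is limited by cause; the second is not.

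Section 2.1 defines patency for plastic drains as "ability to remove plastic biliary drains within 1.5 months of the IRE procedure without need for reinsertion of a drain or stent", and for metal stents as four months free of cholangitis. Section 12.0 also judges plastic drains at 1.5 months. For metal stents it ends the patency period at stent occlusion or death.

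Section 14.1 recommends further study on this condition: "If 10 or more of the 20 patients we plan to enroll display patency", assessed at 1.5 months for plastic and 4 months for metal. (Elsewhere that section prints the plastic time without its decimal point; I read it as 1.5 months.) It also says that only patients who never undergo the procedure are replaced.

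**The concern.** There are two separate difficulties.

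**(a) One window for two endpoints.** A limit of 120 days fits the 4-month metal-stent endpoint. It runs about 75 days past the plastic-drain endpoint (120 − 45). Section 13.0 does not split by drain type, so an event after a plastic-drain patient's assessment can overturn a success already recorded. The 37% control rate for plastic drains is a rate at 1.5 months, so those patients would face a stricter test than the one the null was set for.

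**(b) A limit by cause.** Naming only complication-related withdrawals leaves open how a treated patient is counted who declines further visits, moves to other care or is lost before the endpoint. Whether a withdrawal was due to complications is also a judgement made after treatment in an uncontrolled trial. With 20 patients, one such judgement can decide the recommendation.

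**Working it through.** **Inputs.** From section 14.1: n = 20 ("We will enroll 20 patients"); null rate 37% ("will approximately be 37% and we will use this number as our historical control rate"); alternative 65%; success if at least 10 are patent. Endpoint times are 1.5 × 30 = 45 days (plastic) and 4 × 30 = 120 days (metal). The plan gives neither an expected number of early leavers after treatment nor a plastic/metal mix. I assume 1 to 3 affected patients and show the range.

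**Step 1: the plan's own figures.** The plan states: "This decision rule has 8% Type I error and 12% Type II error for distinguishing between patency rates of 37% and 65" per cent. With X ~ Binomial(20, p), type I error is P(X ≥ r | 0.37) and power is P(X ≥ r | 0.65).

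| Threshold r | Type I error | Power | Type II error |
|---|---|---|---|
| 9 | 30.0% | 98.0% | 2.0% |
| 10 (as written) | 16.5% | 94.7% | 5.3% |
| 11 | 7.8% | 87.8% | 12.2% |
| 12 | 3.1% | 76.2% | 23.8% |

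The stated 8% and 12% fit at least 11, not at least 10. That is a separate matter. Below I use the rule as written as the baseline, and give at least 11 where it matters.

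**Step 2: part (a), plastic-drain successes reset to failure.** If m true successes are reset, the trial needs 10 + m true successes to pass. From the table:
- m = 1: effective threshold 11, power 94.7% → 87.8%, type I error 16.5% → 7.8%.
- m = 2: effective threshold 12, power 76.2%, type I error 3.1%.

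**Step 3: part (b), w treated patients who leave early for other reasons.** The remaining 20 − w patients are observed.
- *Credited as patent:* P(Binomial(20 − w, 0.37) ≥ 10 − w) = 24.0%, 33.5% and 44.9% for w = 1, 2, 3.
- *Counted as failures:* P(Binomial(20 − w, 0.37) ≥ 10) = 12.1%, 8.5% and 5.6%. Power is 91.3%, 86.1% and 78.7%.
- *Removed from the denominator, required count still 10:* the decision is the same as when they are counted as failures. Only the reported rate moves. With 3 removed, 10/20 = 50% (exact 95% CI 27% to 73%) becomes 10/17 = 59% (33% to 82%), and both meet the required count.

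So in part (b) the type I error rises only if leavers are credited as patent.

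**The case against.** The strongest reply is that the decision rule already deals with most of part (b). It requires that "10 or more of the 20 patients we plan to enroll display patency" at the stated times, which is a fixed count. A patient not seen to be patent adds nothing to it, and nothing in the plan drops a treated patient from the denominator. This stands.

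A reader might infer that removing leavers would let a count below 10 pass against a threshold of one half. The documents contain no such proportion threshold; fewer than 10 fails whatever the denominator.

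A reader might also work out the number of early deaths from the 14 to 16 month survival in section 3.0 and treat all of them as unaddressed. That section does not call the figure a median. For metal stents, section 12.0 already ends the patency period at death, so a death before 4 months falls short of the endpoint. Death is not named for plastic drains.

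On part (a), the reinsertion clause has no time limit, and section 9.0 allows plastic drains to be followed by metal stents, so 120 days may be deliberate. The longer window is also conservative, since it can only lower the count. Both observations are fair. But the plan does not say that this is the intention, and section 14.1 fixes the plastic assessment at 1.5 months. The passages conflict as written.

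**Conclusion.** The point holds in two parts of different strength.

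Part (a) follows directly from the text. The rule can turn a plastic-drain success into a failure, at a cost in power of 6.9 points for one patient (94.7 − 87.8) and 18.5 points for two (94.7 − 76.2). It does not raise the type I error.

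Part (b) is a gap in a stated rule, and its effect is conditional. The decision is protected unless early leavers are credited as patent, which the plan neither directs nor forbids. If they are, the type I error rises from 16.5% to between 24.0% and 44.9% for one to three patients. If they are only left out of the denominator, the reported rate is inflated and the decision is unchanged.

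The documents do not support a claim that the plan as written will overstate patency. The sizes rest on exact binomial calculation, the threshold of at least 10, and assumed numbers of affected patients.

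**What to change.** Replace the patency sentence in section 13.0 with:

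> Any treated patient who withdraws, dies or is lost to follow-up before his or her own endpoint time (1.5 months for plastic drains, 4 months for metal stents) without having met the patency definition counts as a failure, whatever the reason. The denominator is all treated patients. Withdrawal after the patient's own endpoint time does not change the result.

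Also state that, for the primary count, the plastic-drain reinsertion clause is assessed up to 1.5 months, in line with section 14.1; otherwise reconcile sections 2.1, 13.0 and 14.1 explicitly.

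This changes counting only, not patient care, and failing early leavers cannot raise the type I error above that of the complete-data rule. The cost is a somewhat lower reported rate, and lower power if early losses are frequent. With 3 of 20 counted as failures and 65% patency in the rest, power falls from 94.7% to 78.7% under at least 10, or from 87.8% to 61.9% under at least 11. If unassessed leavers would have added nothing to the count anyway, failing them costs no additional power.

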14.1 BIOSTATISTICS

The primary objective of this study is to assess biliary drainage patency after IRE treatment of hilar cholangiocarcinoma. In patients with plastic percutaneous drains this is defined as ability to remove plastic biliary drains within 15 months of the IRE procedure without need for reinsertion of a drain or stent. For patients with metal stents in place the definition of patent biliary drainage is 4-months without cholangitis post IRE procedure.

We will enroll 20 patients. Mean patency is approximately 1.5 months for plastic stents and 4 months for metal stents. Assuming an exponential distribution time to failure, we extrapolate that the patency rate at 15 months for plastic stents and at 4 months for metal stents will approximately be 37% and we will use this number as our historical control rate. If 10 or more of the 20 patients we plan to enroll display patency (at 1.5 months for plastic and 4 months for metal stents) then we will recommend IRE for further study. This decision rule has 8% Type I error and 12% Type II error for distinguishing between patency rates of 37% and 65%.

The secondary outcomes of interest are:

- Safety will be assessed by determining the proportion of patients experiencing a clinically relevant complication within 30 days post-IRE, defined as CTCAE (version 5.0) grade 3 or higher complications requiring re-intervention, prolonged hospital stay, intensive care admission, re-admission or leading to mortality. After accruing the first 8 patients, we will do an interim analysis of safety. If 4 or more of these 8 patients experience a grade 3 complication within 30 days post-IRE (as defined above) then the study will stop for lack of safety. A 30 day observation window will follow after the eighth patient is enrolled. If one patient in the first 8 patients has a grade 4 or 5 complication the study will be halted. If none of these conditions are met then we will accrue another 12 patients. If 6 or fewer of the total group of 20 patients have a grade 3 complication we will conclude that the safety endpoint has been met. This safety monitoring rule has an 81% chance of stopping the study early for safety concerns if the true probability of complications is 35%. If there is a death during the 30-day post-procedure period the study will be halted to examine the relationship of death to the procedure. We will examine the cause of death for all 30-day deaths and determine if it could be related to the procedure. If the death can possibly be related to the

procedure then the protocol will be stopped. To continue with the protocol after a death, we will submit to RB all the documentation related to the ascertainment of cause of death and describe how it cannot be related to the RE procedure.

- Duration of hospital stay will be summarized with median, range and quartiles.
- Quality of life will be summarized by average subscale scores at each visit and change from previous visit will also be reported by the same summary statistics.
- Tumor response on CT imaging and blood biomarker response will be reported as a binomial proportion with a 95% confidence interval. RECIST criteria cannot be applied to Klatskin tumors as they are radiographically difficult to assess. This instead will be a subjective evaluation of the ablation zone to determine the appearance of an RE associated ablation zone in the hilar area. This is currently unknown.
- Time between RE and start of palliative chemotherapy will be summarized with median, range and quartiles
- Duration of palliative chemotherapy will be summarized using Kaplan-Meier statistics
- Progression-free and overall survival will be summarized using Kaplan-Meier statistics
- Success rate of completing RE reported as a binomial proportion with a 95% confidence interval

Expected accrual rate, accrual duration, and study duration

Our anticipated accrual rate is approximately 1 patient per month. This accrual rate is based on analysis of potentially eligible patients seen at our Outpatient Clinic in the last 2 years (2016 and 2017). Thus, it should take approximately 1.5 years to accrue the 20 patients needed for the trial. Allowing for 2 months of follow-up to obtain the primary endpoint on the last patient enrolled and 4 months to assemble, analyze and interpret the data the total study duration is projected to be at most 2 years. Patients who consent to the procedure but do not have it will be considered a screen failure. They will be replaced by another patient and their questionnaire data will be removed from the study.

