The primary outcome is patency of biliary drainage. In patients with plastic percutaneous drains this is defined as ability to remove plastic biliary drains within 1.5 months of the IRE procedure without need for reinsertion of a drain or stent. For patients with metal stents in place the definition of patent biliary drainage is 4-months without cholangitis post IRE procedure.

Secondary outcomes are the success rate of completing IRE (defined as percentage of planned pulses completed}, complications, duration of hospital stay, quality of life, impact of IRE on post-procedural CT imaging and blood biomarker response, time between IRE and start of palliative chemotherapy, metal stent patency, progression-free and overall survival. Prolonged hospital stay is defined as hospital stay for more than 10 days. The average length of stay for major liver procedures is 8 days. Patients with hilar cholangiocarcinomas often have biliary drains and stents so require extra care as inpatients after any procedure. Complications will be defined as patients experiencing a clinically relevant IRE-related complication within 30 days post-IRE, defined as CTCAE (version 5.0} grade

3 or higher complications requiring re-intervention, prolonged hospital stay, intensive care admission, re-admission or leading to mortality.

Follow up: 30 days after intervention for the primary endpoint. For survival endpoints, there is a 2-year followup.

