12.0 CRITERIA FOR THERAPEUTIC RESPONSE/OUTCOME ASSESSMENT

The primary endpoint is biliary drainage patency. This will be measured as a marker of therapeutic response. Biliary drainage patency in patients with metal stents is defined as the period between RE treatment and stent occlusion or patient death. Occlusion of the stent is a clinical event. This is defined as recurrent jaundice with cholestasis, cholangitis (fever, increase in serum bilirubin, leukocytosis), stent failure that leads to replacement of a stent, or need to insert a new drain or stent within 4 months. Biliary drainage patency failure in patients that with plastic drains is defined as patients that cannot have plastic drain removed within 1.5 months of the RE.

The patients and caregivers are told about the symptoms of cholangitis and are asked to contact our hospital immediately in case of signs of obstruction. If stent obstruction is suspected, ERC will be performed and stents are changed if necessary.

Tumor response will not be evaluated in this trial by imaging via RECIST criteria as Klatskin tumors are difficult to measure as they are growing along the biliary tract.

Subjective evaluation of the ablation zone to determine the appearance of an RE associated ablation zone in the hilar area will be performed on postoperative scans.

Persistent disease is defined as residual tumor enhancement on the first post-treatment imaging study, and local recurrence is defined as an enhancing tumor within 1 cm of an ablation zone.

As a secondary endpoint we are measuring overall survival. If there is a response to our treatment, we would expect there may be a longer overall survival.

Response on blood biomarker is defined as decrease of blood marker by >20% from the pre-treatment value.

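### The primary endpoint for metal-stent patients has two definitions: a stent replaced within 4 months without cholangitis is a success in section 14.1 and a failure in section 12.0, and the stated follow-up is shorter than 4 months

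*Combined protocol and SAP*

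**What the plan says.** Section 14.1 (Biostatistics) states: "For patients with metal stents in place the definition of patent biliary drainage is 4-months without cholangitis post IRE procedure". The same sentence appears in sections 1.0 and 2.1. It is a yes/no status at 4 months, and cholangitis is the only failure event it names.

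Section 12.0 (outcome assessment) opens by naming biliary drainage patency as the primary endpoint, then says: "Biliary drainage patency in patients with metal stents is defined as the period between RE treatment and stent occlusion or patient death". On occlusion it says: "This is defined as recurrent jaundice with cholestasis, cholangitis (fever, increase in serum bilirubin, leukocytosis), stent failure that leads to replacement of a stent", and it adds the need for a new drain or stent within 4 months.

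The decision rule in section 14.1 recommends further study if at least 10 of 20 patients "display patency (at 1.5 months for plastic and 4 months for metal stents". That fixes the time points but does not say which list of events applies.

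Section 1.0 also lists secondary outcomes that include "time between IRE and start of palliative chemotherapy, metal stent patency, progression-free and overall survival". Metal stent patency is not in the secondary list of section 2.1 and has no analysis in section 14.1.

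On timing, section 1.0 gives 30 days of follow-up for the primary endpoint. The accrual paragraph of section 14.1 allows 2 months for the last patient. Section 13.0 counts withdrawal because of complications before 120 days as a patency failure.

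**The concern.** The trial has a single arm, and its recommendation rests on one count. If two sections score the same patient differently, that count is not determined by the plan. Someone could settle the definition after the outcomes are known, and the error rates stated for the rule would then no longer describe what was done.

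The follow-up statements make this worse. Read literally, neither 30 days nor 2 months is long enough to observe a 4-month endpoint in the last metal-stent patients.

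**Working it through.** **The definitions compared, for a metal-stent patient within 4 months of IRE**

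| Event | Sections 1.0, 2.1, 14.1 | Section 12.0 |
|---|---|---|
| Cholangitis | failure | failure |
| Recurrent jaundice with cholestasis, no cholangitis | success | failure |
| Stent failure leading to replacement, no cholangitis | success | failure |
| New drain or stent needed, no cholangitis | success | failure |
| Death, no cholangitis | not addressed | patency ends |

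Even if jaundice and cholangitis in section 12.0 are read as one joint condition, stent failure leading to replacement remains a separate item, so the conflict stands. Section 13.0 does not settle it, because it covers patients who withdraw and not a patient who has a stent exchanged and stays on study.

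**The plan's own figures.** Inputs from section 14.1 are n = 20, cut-off 10, and rates of 37% and 65%. The 37% reproduces: with exponential failure times and mean patency equal to the time point, exp(−1) = 0.368. The stated errors of 8% and 12% do not reproduce at a cut-off of 10. P(X ≥ 10 | 0.37) = 0.165 and 1 − P(X ≥ 10 | 0.65) = 1 − 0.947 = 0.053. That is a separate matter, and the cut-off is used below as printed.

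**When the decision changes.** If cholangitis means the same in both sections, every section 14.1 failure is also a section 12.0 failure. Let k be the number of patients who succeed in section 14.1 and fail in section 12.0. Then count(12.0) = count(14.1) − k. The two decisions differ when count(14.1) is 10 to 9+k, or equivalently when count(12.0) is 10−k to 9.

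**Chance of a changed decision, X ~ Bin(20, p), k held fixed**

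Point probabilities used:

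| x | p = 0.37 | p = 0.65 |
|---|---|---|
| 7 | 0.1812 | 0.0045 |
| 8 | 0.1730 | 0.0136 |
| 9 | 0.1354 | 0.0336 |
| 10 | 0.0875 | 0.0686 |
| 11 | 0.0467 | 0.1158 |
| 12 | 0.0206 | 0.1614 |

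- Rates taken to describe the section 14.1 count: sum x = 10 to 9+k.
- Rates taken to describe the section 12.0 count: sum x = 10−k to 9.

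| k | Section 14.1 count: 37% / 65% | Section 12.0 count: 37% / 65% |
|---|---|---|
| 1 | 8.8% / 6.9% | 13.5% / 3.4% |
| 2 | 13.4% / 18.4% | 30.8% / 4.7% |
| 3 | 15.5% / 34.6% | 49.0% / 5.2% |

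Both columns are needed because the documents do not say which definition the 37% and 65% belong to, and the choice matters. At k = 3 and 65% the figure is 34.6% on one assumption and 5.2% on the other.

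**Timeline.** The plan's arithmetic is 18 months of accrual + 2 of follow-up + 4 of analysis = 24. With 4 months of follow-up it is 18 + 4 + 4 = 26.

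**The case against.** The best defence is that three sections, including the one that holds the decision rule, agree word for word. An analyst could follow them and treat section 12.0 as the outlier, perhaps as the definition of the secondary outcome metal stent patency named in section 1.0. That is plausible. But section 12.0 calls its endpoint primary, and no section is given precedence.

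A second objection is that the discordant event may be rare. Section 12.0 says "If stent obstruction is suspected, ERC will be performed and stents are changed if necessary", but this follows a sentence about cholangitis symptoms, and an exchange for cholangitis fails under both definitions. The objection stands as to frequency, which is unknown. With no discordant patient the effect is zero. The better evidence that the event was foreseen is that section 12.0 lists replacement as an item apart from cholangitis.

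A third objection is that 4-month status can be ascertained without a new visit. This largely stands. The endpoint consists of dated clinical events, and patients are asked to contact the hospital at once if there are signs of obstruction. Section 10.0 has a visit at about 6 months, a questionnaire at 3 months ± 1 month, and scans every 4 to 6 months. A reader might infer that the data could not be obtained. The documents do not support that; it is the follow-up statements that are wrong.

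**Conclusion.** The conflict is real and must be resolved, because the plan does not determine the primary count for metal-stent patients. Under the shared-cholangitis assumption the section 12.0 count can only be equal or lower, and one discordant patient is enough to reverse the recommendation when the section 14.1 count is exactly 10. The 30-day and 2-month follow-up statements contradict both the 4-month endpoint and the 120-day withdrawal rule.

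The percentages are illustrations and not forecasts. They assume a value of k, hold it fixed although discordant patients are by definition a subset of the section 14.1 successes, and depend on which definition the planning rates describe.

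Two stronger readings should be resisted:

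- A reader might infer that scoring by cholangitis alone favours IRE against the 37% control. The documents do not give the event definitions behind that figure, so neither the direction nor the size of a bias can be stated.
- A reader might infer that counting deaths as failures changes the rule's error rates. At fixed rates and a fixed cut-off the binomial errors do not change. The open question is whether 37% and 65% are still the right rates for the definition chosen.

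**What to change.** Before any patient is scored:

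1. Reconcile sections 1.0, 2.1, 12.0 and 14.1 into one binary metal-stent definition at 4 months for the 10-of-20 count. The sponsor chooses the events and states how a death before 4 months is scored.
2. State whether 37% and 65% remain the right rates for that definition.
3. If the period in section 12.0 is meant as the secondary outcome metal stent patency, label it so and add its analysis to section 14.1.
4. Correct the follow-up statements in section 1.0 and in the accrual paragraph of section 14.1 to 4 months for metal stents. Take 4-month status from dated clinical events at existing contacts or by chart review.

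The cost is wording in four sections and about 2 more months before the primary result (24 becomes 26 months on the plan's own 1.5-year accrual). The observed success rate may be lower if the wider event list is chosen.

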The goals of palliative biliary drainage are to relieve jaundice, prevent cholangitis and liver failure, and improve quality of life [15]. Biliary stents are not without risk and have been associated with occlusion, migration, cholecystitis, and tumor ingrowth and seeding [16]. Successful biliary drainage has obvious palliative advantages to leaving patients undrained due to the morbidity of untreated cholangitis. In addition, in one randomized trial of plastic vs. metal stents, there was a survival advantage with metal stents compared to plastic stents (due to longer patency rates) [17]. Metal stents are a more durable and cost-effective option as they have a patency superior to that of plastic stents, with patients requiring less frequent procedures (Table 1) [18]. Virbidity related to stents can occur even within 30 days of placement (39% plastic stents and 12% metal stents) [19]. Although the overall prognosis of unresectable PHC is poor, patients with locally advanced PHC or lymph node metastases

Table 1. Time of patency (months)

	Plastic stents	Metal stents	P value
Sanachan et al r171	10	3.0	<0.0001
Raiu et al r181	19	5.6	<0.0001

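### The 37% null measures stent patency, so it is unsupported for plastic-drain patients, who are scored on drain removal; separately, the stated error rates do not match the 10-of-20 cut-off

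*Combined protocol and SAP*

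**What the plan says.** Section 14.1 sets a single-arm design of 20 patients with one pooled decision rule: "If 10 or more of the 20 patients we plan to enroll display patency", IRE is recommended for further study. The stated properties are "This decision rule has 8% Type I error and 12% Type II error" "for distinguishing between patency rates of 37% and 65"%. The lower rate is derived in the same paragraph from mean stent patency under an exponential model, and the plan adds "we will use this number as our historical control rate". The background data are the stent patency times in Table 1 of section 3.0.

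The endpoint differs by device. Section 2.1 (repeated in sections 1.0 and 14.1) defines success with plastic percutaneous drains as "ability to remove plastic biliary drains within 1.5 months of the IRE procedure without need for reinsertion of a drain or stent". Section 12.0 defines failure in this group as a drain that cannot come out in that time. Metal-stent patients succeed if they go 4 months without cholangitis.

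No planned split between the groups is given, and section 9.0 leaves the drainage approach before surgery to the surgeon. No reporting of the primary endpoint by device group is specified. Section 14.1 prints 15 months in places for the plastic window; this is read here as 1.5 months with a lost decimal point and is not counted as an error.

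**The concern.** A stent that is open at 1.5 months and a drain that has been taken out by 1.5 months are different outcomes. A drain that is open but still needed would count as patent on the historical measure and as a failure on the trial's endpoint. So 37% does not estimate what would happen to plastic-drain patients if IRE did nothing.

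Both groups go into one count that decides whether IRE is taken forward. If the no-effect removal rate is not 37%, the chance of passing depends on that unknown rate and on how many of the 20 patients have plastic drains. A pass could then consist largely of drain removals with no comparator, and a fail could hide a benefit in metal-stent patients.

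**Working it through.** **Inputs.** From section 14.1: n = 20, pass at 10 or more, rates 37% and 65%, stated errors 8% and 12%, mean patency 1.5 and 4 months. Assumed, because the documents give no value: the number of plastic patients k (5 to 20) and the no-effect removal rate q (10% to 50%).

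**Step 1: the 37%.** With exponential failure, S(t) = exp(−t/mean). At t = mean this is exp(−1) = 36.8% for both stent types. The figure reproduces, as the probability that a stent stays open to its mean patency time.

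**Step 2: the stated error rates.** With X ~ Binomial(20, p), Type I = P(X ≥ r | 0.37) and Type II = P(X < r | 0.65).

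| Cut-off r | Type I | Type II |
|---|---|---|
| 10 or more (as written) | 16.5% | 5.3% |
| 11 or more | 7.75% | 12.2% |

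The rows differ by P(X = 10): 8.75% at p = 0.37 (7.75 + 8.75 = 16.5) and 6.9% at p = 0.65 (12.2 − 6.9 = 5.3). The stated 8% and 12% are the figures for 11 or more. Using exp(−1) for 0.37 gives 16.0% at the written cut-off. A normal approximation there gives 11.4%/8.0% without continuity correction and 16.5%/5.0% with it. None of these yields 8% and 12%.

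**Step 3: the plastic null.** Let A ~ Binomial(k, q) be plastic successes and B ~ Binomial(20 − k, 0.37) metal successes. The exact convolution gives P(A + B ≥ 10) under no effect:

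| Assumed q | k = 5 | k = 10 | k = 15 | k = 20 |
|---|---|---|---|---|
| 10% | 4.4% | 0.6% | <0.1% | <0.1% |
| 20% | 8.0% | 3.2% | 1.0% | 0.3% |
| 30% | 12.6% | 9.4% | 6.8% | 4.8% |
| 37% | 16.5% | 16.5% | 16.5% | 16.5% |
| 45% | 21.6% | 27.4% | 33.9% | 40.9% |
| 50% | 25.1% | 35.5% | 47.1% | 58.8% |

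The 37% row is flat: pooling alone does no harm when the rates are equal.

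**Step 4: Type II error, same rule.** With metal at 65% and k = 10, Type II is 18.0%, 5.3% or 0.8% if the true plastic removal rate after IRE is 50%, 65% or 80%.

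**Step 5: does moving the cut-off cure it?** No. The same convolution at 11 or more with k = 10 gives Type I of 0.1%, 1.0%, 7.75% and 20.6% at q = 10%, 20%, 37% and 50%.

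**Step 6: a source elsewhere in the documents?** The only catheter-free figure (section 3.0, median 305 days) is for IRE-treated patients. The figure for the 137 controls, 59%, is for catheter-related admissions, which is not drain removal.

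**The case against.** The best defence is that this is a small go/no-go screen. The windows of 1.5 and 4 months equal the mean patency times, so both devices share one null by construction and pooling is legitimate. That is sound for patency at those times. It does not carry over to removal, which the patency figures do not measure.

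A reader might infer that the endpoint mismatch, or the pooling, is why the stated 8% and 12% fail. The documents do not support that: those figures fail at the written cut-off even with 37% and 65% in both groups, and pooling equal rates changes nothing. The mismatch leaves the error rates unsupported; the cut-off discrepancy is a separate defect.

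A reader might also infer that the rule is too lenient, pointing to the upper rows of the table. No passage makes a high removal rate without IRE likely. Section 9.0 links removal to obstruction appearing to have been treated, which suggests a low rate and hence a false no-go, but it gives no figure. Neither direction can be shown.

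Comparisons of power must keep to one cut-off. With metal at 65%, plastic at an assumed 20% and 10 patients in each group, the chance of passing is 30% against 95% at 10 or more, or 15% against 88% at 11 or more. Setting 30% against 88% would mix two rules.

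Nor is 37% a clean benchmark for metal-stent patients. Section 14.1 scores them on cholangitis alone, whereas the occlusion definition in section 12.0 also counts recurrent jaundice with cholestasis, stent failure leading to replacement, and a new drain or stent.

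**Conclusion.** The concern holds in two separate parts.

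First, 37% has no documented basis as the null for plastic-drain patients, so the true operating characteristics of the pooled rule are unknown in size and direction. This rests on the definitions in sections 2.1, 12.0 and 14.1 and on the absence of any removal rate without IRE. The percentages in steps 3 to 5 only illustrate the sensitivity; they depend on assumed removal rates and mixes.

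Second, the written cut-off and the stated error rates contradict each other. This needs no assumption beyond the plan's own 37%, 65% and n = 20.

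Neither part shows that the trial will reach a wrong conclusion. They do mean that a pooled pass or fail cannot, as planned, be read as better or worse than historical patency.

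**What to change.** In section 14:

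1. Report the number of plastic-drain and metal-stent patients, classified by device at the time of IRE, and each group's success proportion with an exact 95% CI. Fixing the classification at IRE matters because section 9.0 allows plastic drains to be exchanged for metal stents afterwards.
2. Do not interpret the plastic drain-removal proportion against 37% unless a sourced removal rate without IRE is given. Compare metal-stent patients with 37% only after the metal endpoint in section 14.1 has been reconciled with the occlusion definition in section 12.0.
3. If the pooled rule is kept as a go/no-go screen, state that its error rates assume 37% (null) and 65% (alternative) in both groups. Give the correct figures for the chosen cut-off: 16.5% and 5.3% for 10 or more, or 7.75% and 12.2% for 11 or more. Show them over a range of plastic rates and mixes, as in the table above.

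The cost is wording, two extra proportions and one sensitivity table, with no added patients or procedures. The downside is wide intervals within each group (5 of 10 gives 19% to 81%) and, if the cut-off of 10 is kept, a less favourable stated Type I error.
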